## **2 Study Objectives**

### **2.1 Primary Objectives**

- To characterize the rate of response to azacitidine and sirolimus in adults with high-risk MDS, or relapsed or refractory AML or those unable or unwilling to tolerate high dose chemotherapy.

### **2.2 Secondary Objectives**

- To determine the pharmacodynamic effect of sirolimus on inhibition of mTOR signaling in adults with high-risk MDS, or relapsed or refractory AML or those unable or unwilling to tolerate high dose chemotherapy.
- To determine the safety and tolerability of sirolimus and azacitidine in adults with high-risk MDS, or relapsed or refractory AML or those unable or unwilling to tolerate high dose chemotherapy.
- To determine the progression free survival and overall survival in adults with high-risk MDS, or relapsed or refractory AML or those unable or unwilling to tolerate high dose chemotherapy
- To determine if the quality of life of patients is improved with the combination of azacitidine and sirolimus when compared to historical controls of azacitidine alone.

## **3 Study Design**

### **3.1 General Design**

#### **3.1.1 Therapy timeline**

Refer to section 5.3 for the detailed treatment regimen.

### **3.2 Study Endpoints**

#### **3.2.1 Primary Endpoint**

This study's primary endpoint is to determine the rate of response with azacitidine and sirolimus in adults high-risk MDS, or relapsed or refractory AML or those unable or unwilling to tolerate high dose chemotherapy.

#### **3.2.1.1 Response Criteria**

##### **3.2.1.1 Response Criteria – MDS**

- **Complete Response:**
  - Bone marrow:
    - <5% myeloblasts with normal maturation of all cell lines
    - Persistent dysplasia will be noted
  - Peripheral blood
    - Hgb >11 g/dL
    - Platelets 100x10/L
    - Neutrophils 1.0x10/L
    - Blasts 0%
- **Marrow Complete Response**
  - Bone marrow:
    - 5% myeloblasts and decrease by \_ 50% over pretreatment†
    - Peripheral blood: if HI responses, they will be noted in addition to marrow CR
- **Partial remission**
  - All CR criteria if abnormal before treatment except:
  - Bone marrow blasts decreased by > 50% over pretreatment but still < 5%
  - Cellularity and morphology not relevant
- **Cytogenetic response**
  - **Complete**
    - Disappearance of the chromosomal abnormality without appearance of new ones
  - **Partial**
    - At least 50% reduction of the chromosomal abnormality
- **Hematologic Improvement** - Response criteria responses must last at least 8 weeks and are categorized by cell line impairment at time of diagnosis:
  - **Erythroid response** requires that pretreatment hemoglobin (Hgb) must be Less than 11 g/dL to qualify for response and post-treatment, either:
    - Hemoglobin increase by  $\geq$  1.5 g/dL
    - Relevant reduction of units of RBC transfusions by an absolute number of at least 4 RBC transfusions during 8 weeks compared with the pretreatment transfusion number in the previous 8 weeks. Only RBC transfusions given for a Hgb of  $\leq$  9.0 g/dL pretreatment will count in the RBC transfusion response evaluation
  - **Platelet response** requires pretreatment must be  $< 100 \times 10^9/L$  to qualify for response and post-treatment, either:
    - Absolute increase of  $\geq 30 \times 10^9/L$  for patients starting with  $> 20 \times 10^9/L$  platelets
    - Increase from  $< 20 \times 10^9/L$  to  $> 20 \times 10^9/L$  and by at least 100%
  - **Neutrophil response** requires pretreatment must be  $< 1.0 \times 10^9/L$  to qualify for response and at least 100% increase and an absolute increase  $> 0.5 \times 10^9/L$ .
- **Stable disease**
  - Failure to achieve at least PR, but no evidence of progression for 8 wks
- **Disease progression**
  - For patients with:

- Less than 5% blasts: 50% increase in blasts to 5% blasts
- 5%-10% blasts: 50% increase to 10% blasts
- 10%-20% blasts: 50% increase to 20% blasts
- 20%-30% blasts: 50% increase to 30% blasts
- Any of the following:
  - At least 50% decrement from maximum remission/response in
    - granulocytes or platelets
    - Reduction in Hgb by 2 g/dL
    - Transfusion dependence
  - **Failure**
    - Death during treatment or disease progression characterized by worsening of cytopenias, increase in percentage of bone marrow blasts, or progression to more advanced MDS FAB subtype than pretreatment
  - **Relapse after CR or PR**
    - At least 1 of the following:
      - Return to pretreatment bone marrow blast percentage
      - Decrement of 50% from maximum remission/response levels in
        - granulocytes or platelets
      - Reduction in Hgb concentration by 1.5 g/dL or transfusion dependence

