### 3.2.1.1.2 Response Criteria - AML

- **Complete Remission (CR)**
  - Peripheral Blood Counts -Neutrophil count  $1 \times 10^9/L$ .
  - Platelet count  $\geq 100 \times 10^9/L$ .
  - Reduced hemoglobin concentration or hematocrit has no bearing on remission status.
  - Leukemic blasts must not be present in the peripheral blood.
  - Cellularity of bone marrow biopsy must be  $> 20\%$  with maturation of all cell lines with  $< 5\%$  blasts.
  - Extramedullary leukemia, such as CNS or soft tissue involvement, must not be present.
- **Complete Response in the absence of total platelet recovery (CRp)**
  - Bone marrow ( $<5\%$  blasts) with adequate bone marrow cellularity, no evidence of circulating blasts or extramedullary disease and normalization of peripheral blood counts except for platelets (neutrophil count  $=1,000/\mu L$ ).
- **Partial Remission (PR)**
  - Requires that all of the criteria for complete remission be satisfied except that the bone marrow may contain  $> 5\%$  blasts but  $< 25\%$  blasts. A marrow with  $<5\%$  blasts that contain Auer rods will also be considered a PR
- **Progressive Disease (PD)**
  - An increase of at least 25% in the absolute number of leukemic cells in peripheral blood or bone marrow/aspirate, the development of extramedullary disease, or other evidence of increased tumor burden.
- **Relapse**
  - Relapse following complete remission is defined as: Reappearance of blasts in the blood.
  - Presence of 5% blasts, not attributable to another cause (e.g., bone marrow regeneration).
  - If there are no circulating blasts and the bone marrow contains 5% to 20% blasts, then a repeat bone marrow performed 1 week later documenting more than 5% blasts is necessary to meet the criteria for relapse.

Patients achieving a CR, CRp, or PR will be considered responders. Given the lag between first administration of azacitidine and clinical response, bone marrow examinations will be performed before entry into study, at 6 months, and then at least 6-month intervals afterwards. The biopsies will help

document response to treatment for both MDS and AML patients and to determine endpoints where necessary. Best response will be used for study endpoint.

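### The MDS partial-remission line sets the same blast limit as complete remission, so a marrow that more than halves but stays at 5% or above counts as neither in Arm A

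*Combined protocol and SAP*

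**What the plan says.** All of the MDS wording is in section 3.2.1.1, Response Criteria – MDS.

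- **Complete response.** The marrow must show "<5% myeloblasts with normal maturation of all cell lines". Limits on hemoglobin, platelets, neutrophils and peripheral blasts also apply.
- **Partial remission.** The lead-in is "All CR criteria if abnormal before treatment except", followed by the blast line "Bone marrow blasts decreased by > 50% over pretreatment but still < 5" per cent and the line "Cellularity and morphology not relevant".
- **Stable disease.** "Failure to achieve at least PR, but no evidence of progression for 8 wks".
- **Relapse.** This is headed "Relapse after CR or PR", which treats CR and PR as the MDS responses.

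Marrow CR, cytogenetic response and hematologic improvement are also listed for MDS. The section does not say whether any of them counts as a response for the primary endpoint.

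The AML criteria (section 3.2.1.1.2) build PR in the same way: "Requires that all of the criteria for complete remission be satisfied except that the bone marrow may contain" blasts above 5% and below 25%. The only sentence naming responders (CR, CRp or PR) closes that AML section. Its paragraph goes on to cover both diseases and makes best response the study endpoint. Marrow examinations are required at entry and at least every 6 months.

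Section 7.1 sets the Arm A rule. The null rate is 23% and the target 40%. The arm stops if 3 or fewer of 14 respond, and the drug is rejected if 12 or fewer of 40 respond.

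**The concern.** An exception to a CR criterion should let through something that CR does not. On blasts, this one repeats the CR limit. A patient whose marrow blasts fall by more than half, whose counts recover and whose best marrow stays at 5% or above therefore has no response category. Such a patient is what a PR built as CR with residual disease would normally describe.

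Response rate is the primary endpoint, and the loss falls on the only arm still enrolling. The planned total of 74 in the Study Summary equals 40 for Arm A plus the 27 and 7 accrued before Arms B and C closed. Arm A is thus still planned to 40 and its final rule still applies. If CR and PR are the MDS responders, Arm A can be undercounted at both looks, and the trial could reject an active regimen because of a misprinted sign.

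**Working it through.** **Step 1. Who falls in the gap.** Let b be pretreatment blasts and m the best later value, with counts recovered. The gap needs m < 0.5b and m ≥ 5%, so b > 10%.

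| Pretreatment → best | Fall | CR (m < 5%) | PR as printed (fall > 50% and m < 5%) |
|---|---|---|---|
| 12% → 5% | 58% | no | no |
| 15% → 6% | 60% | no | no |
| 18% → 7% | 61% | no | no |
| 19% → 8% | 58% | no | no |
| 12% → 4.9% | 59% | blast limit met | blast limit met |

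Arm A admits patients with more than 5% blasts (section 4.1). The progression criteria foresee patients who start above 10%, for example "10%-20% blasts: 50% increase to 20% blasts".

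PR as printed is not empty. It waives cellularity and morphology, so it captures a patient with blasts below 5%, recovered counts and abnormal maturation.

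**Step 2. Reproduce the Arm A design.** Inputs from section 7.1: n1 = 14, stop if X1 ≤ 3; n = 40, reject the drug if the total is ≤ 12; rates 0.23 and 0.40.

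- P(stop at stage 1) = Σ C(14,x) p^x (1−p)^(14−x), for x = 0 to 3.
- P(declare active) = Σ P(X1 = x) × P(X2 ≥ 13 − x), for x = 4 to 14, with X2 binomial(26, p).

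At p = 0.40, P(stop) = 0.0008 + 0.0073 + 0.0317 + 0.0845 = 0.124, and P(declare) = 0.800. At p = 0.23, P(stop) = 0.592, P(declare) = 0.090, and the expected size is 14 + 26 × (1 − 0.592) ≈ 24.6. These match the plan.

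**Step 3. Effect of losing the gap patients.** The documents give no frequency, so the loss is an assumed range. It also assumes that the 40% target counts these patients as responders.

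| Points lost from 40% | Expected patients of 40 | Counted rate | P(stop at stage 1) | Power | Drop in power |
|---|---|---|---|---|---|
| 0 | 0 | 0.40 | 0.124 | 0.800 | – |
| 1 | 0.4 | 0.39 | 0.141 | 0.768 | 0.032 |
| 2 | 0.8 | 0.38 | 0.158 | 0.732 | 0.068 |
| 5 | 2 | 0.35 | 0.220 | 0.607 | 0.193 |

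As shares of the target responders, the losses are 1/40 = 2.5%, 2/40 = 5% and 5/40 = 12.5%.

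If the corrected definition keeps everyone the printed PR line captures, the as-written count can never exceed the corrected count. The drop in power is then also the probability that the two definitions give opposite conclusions: 0.03, 0.07 or 0.19.

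**Step 4. Under the null.** If the 23% rate loses 1 or 2 points as well, P(declare) falls from 0.090 to 0.068 (p = 0.22) or 0.050 (p = 0.21).

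**The case against.** - **The sign may come from reading the PDF.** Several comparison signs in this section are lost, for example in the CR platelet and neutrophil limits and the marrow CR line. Those signs are missing, whereas here one is printed. The words around it (an exception, then a residual value) and the AML band above 5% suggest it is reversed. The cause is still unproven, so checking the source file comes first.
- **The AML comparison is not all one way.** AML PR also admits a marrow below 5% that contains Auer rods, so a PR below the CR limit on morphological grounds is not foreign to this protocol. That supports keeping the patients the printed MDS line captures. It does not explain why residual blasts of 5% or more are shut out.
- **The direction of the error is conditional.** If PR were simply changed to residual blasts of 5% or more, patients with blasts below 5% and abnormal maturation could drop out, and the as-written count could exceed the corrected one. The one-sided reading holds only if the correction keeps them.
- **The MDS responder set is not defined.** If hematologic improvement counts, many gap patients would already be responders and the loss shrinks. The recovery would not always qualify: platelets rising from 80 to 105 × 10⁹/L fall short of the required increase of 30.
- **The size is assumed and its starting point is not secure.** Since October 2017 Arm A has admitted previously treated MDS, a group for which Arm C used 5% against 20%, so 40% may be optimistic. Stage 1 may also be past. Given that it was passed, power is 0.800/(1 − 0.124) = 0.91, and 0.89, 0.87 or 0.78 after the assumed losses, so the drops are 0.02, 0.04 or 0.14.
- **The scope is narrow.** Only patients entering above 10% blasts who never get below 5% are affected, and best response rescues anyone who later meets CR.

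These points limit the size of the effect. None closes the gap in the printed definition.

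**Conclusion.** The definition is wrong as written: its blast exception repeats the CR limit, and a clear group of Arm A patients has no response category. It should be fixed, because it feeds the primary endpoint and both decision limits of the only open arm.

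The size is uncertain. An assumed loss of 1 to 5 points lowers power from 0.80 to between 0.77 and 0.61, or by 0.02 to 0.14 if stage 1 has already been passed. This rests on three assumptions: CR and PR are the MDS responders, the 40% target includes these patients, and none of them is recovered through another category. Provided the correction keeps everyone the printed line captures, the error runs only towards rejecting an active regimen and cannot create a false claim of activity.

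Confidence is high about what the text says and what follows from it. It is lower about why the sign is there. The documents do not show how any patient was actually scored.

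**What to change.** 1. Check the sign against the sponsor's source file. If it is confirmed as printed, correct the MDS PR blast line to a fall of more than 50% over pretreatment, as now, with residual blasts of 5% or more.
2. State how a marrow with blasts below 5%, recovered counts and persistent dysplasia or abnormal maturation is classed, so that no patient the printed PR line captures is lost.
3. Name the MDS categories that count as response (including whether marrow CR and hematologic improvement do), consistent with the basis of the 23% and 40% rates.
4. Date the change and state, before any re-scoring, that the corrected definition governs the 3 of 14 and 12 of 40 rules.
5. Re-score all Arm A patients, stage 1 included, from recorded blasts and counts using best response. Report the as-written rate as a sensitivity analysis.

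The cost is a few lines of protocol text and re-scoring from data already collected, with no new patients or procedures. The drawback is that an endpoint definition changes in an open-label trial with some outcomes known. That is why the dating, the order of steps 4 and 5 and the reporting of both rates matter.

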#### ***The following will be considered toxicities***

- Non-hematologic toxicity is defined as Any Grade III or Grade IV non-hematologic toxicity attributable to the investigational drug with the specific exclusion of:
  - a. Grade III nausea and vomiting responsive primarily to non-parenteral anti-emetics, intermittent use of parenteral anti-emetics is acceptable.
  - b. Grade III fever or infection
  - c. Splenic Infarction
  - d. Grade III/IV Tumor lysis syndrome
  - e. Grade III/IV metabolic abnormalities attributable to anti-fungal medication or tumor lysis syndrome that is correctable with IV or PO supplementation.
  - f. Grade III/IV stomatitis that resolves within 14 days of neutrophil recovery
  - g. Grade III/IV hypercholesterolemia / hypertriglyceridemia
  - h. Grade III hyperbilirubinemia and/or transaminitis that resolves to less than or equal to a grade II toxicity within 14 days.

Hematologic toxicity: Marrow aplasia (defined as <10% cellularity with <10% blast) > 4 weeks not attributable to disease. All unanticipated > Grade 2 non-hematologic AE's will be reported. The only hematologic event which will be considered an AE/SAE for this study is marrow aplasia (defined as <10% cellularity with <10% blast) > 6 weeks not attributable to disease and this will be reported. There is no degree of neutropenia, anemia, or thrombocytopenia that would qualify as an AE/SAE as the purpose of the treatment is to create a period of complete aplasia in the marrow.

- Blood product transfusion will not be considered a limiting toxicity, since these patients require frequent transfusions secondary to disease process.
- Toxicity requiring discontinuation of therapy or removal of the patient from the study.
- Death resulting from toxicity attributed to the combination of sirolimus and azacitidine.

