#### **4.4 Early Withdrawal of Subjects**

##### **4.4.1 When and How to Withdraw Subjects**

Subjects will continue on study treatment unless the following occurs:

1. Unacceptable toxicity. See section 3.2.2.1 for details.
2. Non-compliance by the patient with protocol requirements
3. Changes in medical status of the patient such that the patient no longer meets eligibility requirements or the investigator believes that the treatment is no longer in the patient's best interest.
4. Patient refusal
5. Disease Progression
6. Alternative therapy is started as per the discretion of the physician, for example, bone marrow transplant.

The discontinuation of study treatment will not constitute study withdrawal or study completion. In the event of a decision to discontinue treatment, the treatment phase will be considered complete and the follow-up phase will begin.

If a subject discontinues treatment and actively withdraws consent, no additional data will be collected.

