### 5.3.2 Dose Reductions

Standard dose reductions for Azacitidine will occur as follows:

If blood counts at time of baseline PD draw WBC  $\geq 3.0 \times 10^9/L$ , ANC  $\geq 1.5 \times 10^9/L$ , and platelets  $\geq 75.0 \times 10^9/L$  adjust the dose as follows, based on nadir counts for any given cycle:

Nadir Counts		% Dose in the Next Course
ANC (<math>\times 10^9/L</math>)	Platelets (<math>\times 10^9/L</math>)	
<0.5	<25.0	50%
0.5 – 1.5	25.0-50.0	67%
>1.5	>50.0	100%

For patients whose baseline counts are WBC  $<3.0 \times 10^9/L$ , ANC  $<1.5 \times 10^9/L$ , or platelets  $<75.0 \times 10^9/L$ , dose reductions will be at the discretion of the treating physician.

At the discretion of the treating physician cycles may be spaced out to up to 42 days apart based upon hematologic response and recovery between cycles.

Renal Toxicity - If unexplained reductions in serum bicarbonate levels to  $<20$  mEq/L occur, the dosage should be reduced by 50% on the next course. If increases in BUN or serum creatinine (unexplained) occur, delay next cycle until values reach baseline or normal, then reduce dose by 50% for next treatment course.

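### MDS progression and relapse by blood count carry no timing or attribution condition, so an expected treatment nadir in an Arm A responder can be read as progression

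*Combined protocol and SAP*

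**What the plan says.** Section 3.2.1.1 (MDS) lists the non-blast items for progression so that any one is enough: "At least 50% decrement from maximum remission/response in" granulocytes or platelets, a 2 g/dL haemoglobin fall, or transfusion dependence. Relapse after CR or PR also needs only one item. Its list has return to the pretreatment marrow blast percentage, a 50% fall in granulocytes or platelets from best level, and "Reduction in Hgb concentration by 1.5 g/dL or transfusion dependence". No time window, repeat test or cause is attached to the count, haemoglobin or transfusion items.

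Conditions of this kind do appear nearby. In the AML criteria (3.2.1.1.2), one relapse item reads "Presence of 5% blasts, not attributable to another cause (e.g., bone marrow regeneration"), and for 5% to 20% marrow blasts without circulating blasts "a repeat bone marrow performed 1 week later documenting more than 5% blasts is necessary to meet the criteria for relapse". MDS haematologic improvement must last at least 8 weeks.

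Elsewhere the protocol expects low counts from treatment. Section 3.2.2.1 says that "the purpose of the treatment is to create a period of complete aplasia in the marrow" and accepts no degree of neutropenia, anaemia or thrombocytopenia as an adverse event. Section 5.3.2 tells the physician to "adjust the dose as follows, based on nadir counts for any given cycle" and adds that "cycles may be spaced out to up to 42 days apart based upon hematologic response and recovery between cycles". Section 4.4.1 opens its list with "Subjects will continue on study treatment unless the following occurs"; disease progression is the fifth entry.

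**The concern.** A single blood count can carry two opposite instructions. Under 5.3.2 a deep nadir leads to a smaller next dose and continued treatment. Under 3.2.1.1 with 4.4.1 the same nadir, in a patient who has responded, is progression and a reason to stop.

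Two things are at stake. A patient who is benefiting could lose the regimen because of its expected effect on the marrow. The event dates behind PFS (2.2) and the Kaplan-Meier curves for time to progression and time to relapse (7.2) could also be set at a nadir and not at the return of disease. If treating physicians or chart abstractors apply different unwritten rules, these curves would mix two definitions. Arm A is the only arm still open (4.1), and it is the arm that uses the MDS criteria.

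**Working it through.** The plan gives no nadir rate and no estimate of misclassification, so there is no figure of its own to reproduce. The check compares the rules and uses simple arithmetic.

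**Inputs**
- MDS CR floors (3.2.1.1): platelets 100, neutrophils 1.0. The sign and exponent are lost in the extracted text; I read both as minimum values in ×10⁹/L. Haemoglobin must exceed 11 g/dL.
- Dose table (5.3.2): ANC <0.5 or platelets <25 gives 50% of the dose; ANC 0.5–1.5 or platelets 25–50 gives 67%. It applies when baseline WBC is at least 3.0, ANC at least 1.5 and platelets at least 75. Otherwise reductions are at the physician's discretion.
- Labs (Attachment 2, footnotes 10, 17, 18): pre-cycle labs for every cycle; twice weekly on treatment in cycles 1–6, then weekly if disease is stable; weekly off treatment (days 11–28) in cycles 1–6, then discretionary if stable.
- Marrows (footnote 9): every 6 months from enrolment ±10 days, or sooner at discretion. I take enrolment as Day 1 and the first scheduled response marrow as Day 183.

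**1. Which nadirs meet the rule.** Decrement = 1 − nadir/best.
- Platelets, best 100: nadir 50 gives 1 − 50/100 = 50%; nadir 25 gives 1 − 25/100 = 75%. A higher best value makes the fall larger. Every platelet nadir in either reduced-dose band therefore qualifies in a CR patient.
- ANC, best 1.0: nadir 0.5 gives 1 − 0.5/1.0 = 50%. Every nadir in the <0.5 band qualifies. All of the 0.5–1.5 band qualifies only if the best ANC was 3.0 or more (1 − 1.5/3.0 = 50%).
- Haemoglobin: a fall from just above 11 to just above 9 meets progression (11 − 2 = 9), and to just above 9.5 meets relapse (11 − 1.5 = 9.5).
- Transfusion dependence need not be new. A patient dependent at entry meets the progression item from the start if it is read literally.

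**2. What each section does with one such count**, for example platelets of 40 after a CR:

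| Section | Result |
|---|---|
| 3.2.2.1 | not an adverse event |
| 5.3.2 | 67% of the dose next course, continue |
| 3.2.1.1 (MDS) | progression, and relapse after CR |
| 4.4.1 | progression is a reason to stop |

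**3. When a responder is exposed.** The count items need an earlier best response. The last scheduled weekly off-treatment CBC falls on day 28 of cycle 6, that is 5 × spacing + 28.
- 28-day cycles: 5 × 28 + 28 = Day 168, before the Day 183 marrow.
- 42-day cycles: 5 × 42 + 28 = Day 238, which is 238 − 183 = 55 days after it (45 to 65 over the ±10-day window).
- Break-even: 5L + 28 > 183 gives L > 31 days (29 for a Day 173 marrow, 33 for Day 193).

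On the default cycle, then, the densest nadir sampling ends before the first scheduled response marrow. Exposure remains through wider spacing, an earlier discretionary marrow, on-treatment and pre-cycle labs after cycle 6, and the nadir counts that 5.3.2 needs in any cycle.

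**4. How many could be at risk.** If Arm A enrols 40, the design rates give 0.23 × 40 = 9.2 to 0.40 × 40 = 16 responders. This brackets those to whom the relapse rule could apply, assuming that each is a CR or PR. It is not a count of patients misclassified.

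**The case against.** The strongest reply is that the protocol, read as a whole, already shows that a nadir is not progression: 5.3.2 manages it and gives the next course. That is probably what the authors meant, and nothing in the documents shows that any patient was stopped or misdated. It stands as a limit on the claim. It does not close the gap, because 3.2.1.1 never says so and no other section adds the condition.

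A reader might infer that the true progression date would be lost for good. Attachment 2, footnote 12, does stop disease-status follow-up at relapse or progression, and footnote 9 ends scheduled marrows. But section 6 follows patients for disease status and survival for 5 years after the last enrolment, with no stop at progression, and 4.4.1 says that stopping treatment is not study withdrawal. The two follow-up statements conflict, so irrecoverable loss is not established.

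A reader might also take AML to be fully protected. It is not: the safeguards cover marrow-blast relapse only. Reappearance of blood blasts and AML progressive disease have no confirmation step, and AML relapse uses no count criterion at all.

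Two further limits stand. Section 4.4.1 lists progression but not relapse, so treatment stops only because the same fall also meets progression. The extracted progression bullets are nested, and some may read them as needing a blast rise as well; the relapse list leaves no such doubt.

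**Conclusion.** The point holds as a missing condition that brings 3.2.1.1 and 5.3.2 into conflict. Read literally, an expected nadir in an Arm A responder is progression. That could end treatment too early and place PFS, time to progression and time to relapse too early.

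The size in patients or months cannot be estimated: the documents give no nadir rate, and any per-cycle probability would be invented. The thresholds (platelets ≤50, ANC <0.5 after a CR) rest on reading the CR floors as minimum values.

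The primary result should not be inferred to be at risk. It uses best response, so a later nadir does not undo a documented response. The Simon decision and overall survival are not directly affected either. This is a cheap improvement to descriptive secondary endpoints and to a stopping rule.

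**What to change.** In 3.2.1.1 (MDS), add wording such as:

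- Progression or relapse based on counts, haemoglobin or transfusion must not be explained by study treatment, infection or bleeding. It must be present on a pre-cycle (recovery) CBC or, if no new cycle starts, on the first available CBC after Day 42. The event is dated to that CBC.
- Transfusion dependence must be new relative to best response or, if there was no response, to the 8 weeks before treatment.
- If death or new anti-leukaemic therapy comes before a recovery CBC, the event is classified from the available data; death counts as a PFS event.

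In 4.4.1, add that a nadir managed under 5.3.2 is not by itself progression. Leave blast-based progression, discretionary marrows and the investigator's discretion to stop unchanged.

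I would not require a second confirmatory CBC. Section 6 allows follow-up by phone or chart review, so an off-treatment repeat might never exist and real events could be lost.

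Cost: protocol wording, with no new visit, test or sample-size change, since pre-cycle labs are already required (Attachment 2, footnote 10). Attribution stays a judgement while treatment continues; the recovery CBC makes it less subjective. The downside is that a count-only progression may be recognised up to about one cycle (28–42 days) later. A discretionary marrow or the investigator's right to stop can shorten that delay.
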